1 STUDY SUMMARY

Clinicaltrial Id:

Title of Study: Pilot implementation of HIV self-testing delivery in private pharmacies combined to a Respondent Driven Sampling method to improve HIV testing for MSM and TGW in Phnom Penh

Short title - Sponsor N°: -ANRS 0100s

Sponsor: Institut national de la santé et de la recherche médicale - ANRS Emerging Infectious diseases (Inserm-ANRS| MIE)

Coordinating Investigator(s):

[name], University of Health Sciences, Cambodia

[name], SESSTIM, France

Participating countries: CAMBODIA AND FRANCE

Primary objective:

Evaluate the feasibility of HIV self-testing (HIVST) delivery by a private pharmacy network among men who have sex with men (MSM) and transgender women (TGW) recruited through a classic and digital Respondent Driven Sampling method to improve HIV testing in Phnom Penh, Cambodia

Secondary objectives:

- Evaluate the acceptability and appropriateness of the strategy
- Identify barriers and facilitators
- Estimate the linkage to confirmatory testing for those with a reactive test and linkage to HIV care and ART for those with a positive confirmatory HIV test
- Estimate linkage to pre-exposure prophylaxis (PrEP) services for negative participants
- Estimate the characteristics of participants and compare to those reported in Integrated Biological and Behavioral Survey (IBBS 2019) for MSM and TGW in Cambodia
- Evaluate the adherence of participants to a 6-monthly repeated HIV testing

Methodology:

An interventional pilot study using a mixed qualitative and quantitative approach will be carried out in order to evaluate the feasibility, acceptability and appropriateness of the strategy and to identify barriers and facilitators.

The participant recruitment method will be designed as a Respondent Driven Sampling (RDS) by recruiting initial seeds both at hotspots and on social networks. Prior to seed recruitment, a consultative meeting will be conducted in order to optimise the selection criteria of the seeds. The seeds will then distribute electronic and paper coupons to their networks physically and via social media, messaging and calling applications such as Twitter, Whatapp and Telegram (e-coupons).

Version 1.1 du 18/04/2022

Each recruited participant will bring the coupon to be scanned at partner pharmacies to receive direct and free access to one HIVST kit. Partner pharmacies with a proper dedicated room/space securing privacy and secrecy in Phnom Penh are the study sites. There, trained community workers who get notified by partner at each visit of participant will do the study visit including information/consent (annexe 1 and 2), e-CRF filling (annexe 3) and give a link of an external website to send the HIV test results and receive information or advices. These recruited individuals will be considered as wave 1 of recruitment and will each receive 10 additional coupons to recruit the members of their networks. The next round of individuals recruited and enrolled will be considered as wave 2, and so on.

After 6 months, a qualitative assessment via focus groups will be conducted among MSM, TGW and pharmacists to evaluate feasibility, acceptability and appropriateness of the intervention and to identify barriers and facilitators.

Several ART sites/HIV clinics particularly in charge of key populations will be specifically selected as participating centers in order to collect information on linkage to care or prevention services for positive and negative participants, respectively.

Each participant will be followed during 18 months and encouraged to perform a 6-monthly HIV testing during this period.

Expected enrolment

A pragmatic approach is carried out in which the enrolment will be stopped at the end of the inclusion period or if the number of participants reaches a maximum of 1500.

Outcomes

With regard to the novel intervention, the outcomes will focus on its feasibility, adoption, acceptability and appropriateness.

The primary outcomes will be the HIV self-testing uptake defined as the number of HIV self-tests delivered / total number of coupons distributed

The secondary outcomes will be:

- Proportion of HIVST result's recorded / total number of HIVST delivered
- Proportion of paper and electronic coupons delivered and recorded
- Number of HIV tests realized / number of HIV tests results non recorded
- Proportion of MSM/TGW with positive HIV self-tests linked to an ART site
- Proportion of negative MSM/TGW linked to PrEP services
- Characteristics of participants recruited (sociodemographic, sexual behavior, utilization of dating application, substance use) in comparison with IBBS 2019 report
- Proportion of participants with 6-monthly repeated HIV testing during 18 months

Outcomes of acceptability and appropriateness will be explored during focus groups: comfort, usefulness, suitability, confidentiality, credibility, advantages and barriers.

Version 1.1 du 18/04/2022

Eligibility

Inclusion criteria

- To be aged from 18 years old (legal age in Cambodia)
- For MSM, to have at least one oral or anal intercourse with another man in the past 12 months
- For TGW, to be biologically a male at birth and self-identified as a woman or third gender and have at least one oral, anal or vaginal intercourse with another man in the past 12 months

Non-inclusion criteria

Known HIV positive status

Statistical methods

We want to evaluate the feasibility of the intervention to improve HIV testing among MSM and TGW in Phnom Penh. We will use a pragmatic approach with the objective to recruit the maximum of MSM and TGW. According to the IBBS 2019, the estimated number of MSM in Phnom Penh is 6300 and the estimated number of TGW is 1400.

With 1500 participants (1000 MSM and 500 TGW), we will be able to estimate an HIV self-test uptake of 70% to within a 95% confidence interval of +/- 2 – 2.5% (width of the confidence interval (in %) = $1.96 \times \sqrt{(p \times (1-p)/n)}$).

Estimated planning or study timetable

- Protocol submission: December 2022
- Study implementation: February 2023 July 2023
- Data collection: August 2023 April 2025 (18 months)
- Duration of the study: 24 months

Version 1.1 du 18/04/2022

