These recruited individuals will be considered as wave 1 of recruitment and will each receive 10 additional coupons to recruit the members of their networks. The next round of individuals recruited and enrolled will be considered as wave 2, and so on. The number of 10 coupons was selected to avoid a bias risk related to participation incentives.

To facilitate the return of HIVST kit results, participant will upload the picture of results labeled with their identifier directly using the link of the external website that they received from community worker/research team during their visits at pharmacy. In case of any question, they could reach community worker/research team by hotline number. According to the results, the participants will be proposed with a support for linkage to confirmatory test or to PrEP services. Each non-reactive participant will be provided another new coupon (paper or electronic format upon their preference) with a reminder to perform a 6-monthly HIV testing during 18 months. They will not be granted any token or incentives if they fail to return the result of HIVST kit taken at pharmacies. These incentives are also added upon the number of recruited members of their networks using common money transfer and payment services in Cambodia such as Wing, TrueMoney.

After 6 months, a qualitative assessment will be conducted to evaluate feasibility, acceptability and appropriateness of the intervention and to identify barriers and facilitators.

Several ART sites/HIV clinics particularly in charge of key populations will be specifically selected as participating centers in order to collect information on linkage to care or prevention services for positive and negative participants, respectively.

Tentative study agenda

- Protocol submission: December 2022
- Study implementation: February 2023 July 2023
- Data collection: August 2023 April 2025 (18 months)
- Duration of the study: 24 months

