7 STUDY ENDPOINTS

Primary endpoint

 HIV self-testing uptake defined as the number of HIV self-tests delivered / total number of coupons distributed

Secondary endpoints

- Proportion of HIVST result's recorded / total number of HIVST delivered
- Proportion of paper and electronic coupons delivered
- Number of HIV tests realized / number of HIV tests results non recorded
- Proportion of MSM/TGW with positive HIV self-tests linked to an ART site
- Proportion of negative MSM/TGW linked to PrEP services
- Characteristics of participants recruited (sociodemographic, sexual behavior, utilization of dating application, substance use) in comparison with IBBS 2019 report
- Proportion of participants with 6-monthly repeated HIV testing during 18 months

Outcomes of acceptability and appropriateness will be explored during focus groups: comfort, usefulness, suitability, confidentiality, credibility, advantages and barriers.

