with the important details about the study. Once consent to the study, the seed is provided with two types of coupons for HIVST kit at partner pharmacy: 1- 5 electronic coupons (e-coupons) consisting of a pictured unique anonymous QR code and identifier and address of partner pharmacies 2- 5 paper coupons consisting of a printed unique anonymous QR code, identifier and address of partner pharmacies. The seeds will provide paper- and e-coupons to their networks physically and via social media, messaging and calling applications such as Twitter, Whatapp and Telegram (e-coupons). For online application and social media, a peer could be reached by chat or call.

When the participant arrives in a partner pharmacy, the coupon (unique QR code with identifier) will be scanned by the pharmacist prior to the free delivery of HIV self-test. Community workers (CWs) will be then alerted by the pharmacist for study visits to participant directly at the dedicated space at the pharmacy. During the visit with CW, participant will:

- Receive the information about the study
- Receive an ID
- Check for eligibility criteria
- Be requested for his/her consent to participate in the study and to different specific consents as receiving funds, being recontacted by phone and participation in FGD
- Fill in the detailed e-CRF for sociodemographic status, sexual behaviors, utilization of dating application, substance use, knowledge about PrEP and willingness to pay for HIV self-testing by using Tablet with the eventual assistance from a community worker
- Receive the information on HIV self-testing instructions, list of partner pharmacies, helpline phone number, location of the 2 partners ART sites, location of the HIV clinics with prevention services and PrEP delivery availability
- Be provided one free HIV self-testing kit delivered
- Receive the link of the external website to performance HIV test, interpret and send the HIV test result, receive necessary information and in case of non-reactive, to receive another coupon for 6-monthly test during 18 months
- Receive 10 (paper or electronic) coupons to distribute to peers
- Be asked if the participant would agree to be recontacted for an eventual participation in a focus group

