14 STATISTICAL ANALYSES

Calculation of number of participants needed

We will use a pragmatic approach with the objective to recruit the maximum of MSM and TGW. According to the IBBS 2019, the estimated number of MSM in Phnom Penh is 6300 and the

Version 1.1 du 18/04/2022

estimated number of TGW is 1400.

With 1500 participants (1000 MSM and 500 TGW), we will be able to estimate an HIV self-test uptake of 70% to within a 95% confidence interval of +/- 2 – 2.5% (width of the confidence interval (in %) = $1.96 \times \sqrt{(p \times (1-p)/n)}$.

Analysis plan

Description of the characteristics at inclusion.

These variables will be described by their median, interquartile range, mean, standard deviation, or frequencies (%), as appropriate. These variables will be compared to those reported in the IBBS 2019 for MSM and TGW.

Primary outcome

The percentage, and its 95% confidence interval of HIV self-tests delivered among the total number of coupons distributed will be given and stratified by gender (MSM or TGW) and by type of coupons (paper or electronic).

Secondary outcomes

- The percentage and its 95% confidence interval of HIVST result's recorded among the total number of HIVST delivered will be given and stratified by gender (MSM or TGW)
- For those accepting to be contacted by phone, the percentage and its 95% confidence interval of HIVST realized among the number of HIV tests results non recorded will be given
- The percentage and its 95% confidence interval of participants with positive HIV selftests linked to an ART site will be given and stratified by gender (MSM or TGW)
- The percentage and its 95% confidence interval of participants with negative HIV selftests linked to PrEP services will be given and stratified by gender (MSM or TGW)
- The percentage and its 95% confidence interval of participants with 6-monthly repeated HIV testing during the 18 months (so 4 HIVSTs during the total duration of the study) will be given
- The probability of discontinuation of HIV testing and its 95% confidence interval, as well as the median time to the occurrence of HIV testing discontinuation, will be determined using a Kaplan Meier analysis, to take into account censored data due to lost of follow-up.

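### If every issued recruitment coupon is counted, primary uptake cannot exceed about 10% and is about 9.9% at the 1500 cap for any redemption rate that reaches it

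*Protocol*

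**What the plan says.** Protocol section 7 sets the primary endpoint as "HIV self-testing uptake defined as the number of HIV self-tests delivered / total number of coupons distributed". Section 14 (Primary outcome) analyses it the same way, as a percentage with its 95% confidence interval of "HIV self-tests delivered among the total number of coupons distributed", stratified by gender and by paper or electronic coupon.

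Coupon supply is fixed per person. Section 5 (Study overview) gives each of 15 initial seeds 5 electronic and 5 paper coupons. Of those they recruit it says: "These recruited individuals will be considered as wave 1 of recruitment and will each receive 10 additional coupons to recruit the members of their networks". This rule then repeats: "The next round of individuals recruited and enrolled will be considered as wave 2, and so on". Section 9 lists the same step at the pharmacy visit: "Receive 10 (paper or electronic) coupons to distribute to peers". It also allows further seeds later, without giving a number.

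Section 1 (Expected enrolment) states the stop: "the enrolment will be stopped at the end of the inclusion period or if the number of participants reaches a maximum of 1500".

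Section 14 plans on an uptake of 70% with 1500 participants and a precision of about 2 to 2.5 points. The visible text has no rule to reduce or halt coupon issue before the stop, no coupon validity period, no period of continued redemption after the stop, and no exclusion of open coupons from the denominator.

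**The concern.** Every redeemed recruitment coupon brings in one enrolee, and every enrolee brings ten new coupons into the denominator. The denominator therefore grows ten times as fast as the numerator. When enrolment stops, the most recent coupons have had little or no time to be used, yet they count as not taken up. The faster the chains grow, the larger the share of coupons cut off this way.

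The primary endpoint is meant to answer the feasibility question. If its value is set by the 10-coupon rule and the stopping rule, a strategy that peers embrace and one that they use sparingly would report the same overall figure. Both would look like a large shortfall against the planned 70%, with a narrow confidence interval around a number that says little about peers' behaviour.

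**Working it through.** **Inputs.** Seeds S = 15 and 10 coupons per seed (section 5); 10 coupons per enrolee (sections 5 and 9); cap N = 1500 (section 1); planned uptake 70% with n = 1500, and population estimates of 6300 MSM and 1400 TGW (section 14). Assumptions: *distributed* means issued to seeds and enrolees; repeat-test coupons and kits are not counted; each kit in the numerator goes to one enrolee.

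**The plan's own figure.** 1.96 × √(0.70 × 0.30/1500) = 2.32 points, inside the stated 2 to 2.5. It reproduces, with participants as n.

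**Counting identity.** Each non-seed enrolee redeems one coupon and everyone enrolled receives ten:

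uptake = (N − S)/(10N) = 0.10 − S/(10N).

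The true redemption rate p appears only through N.

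- At the cap with seeds inside it: 1485/15,000 = 9.9%.
- Seeds outside the cap: 1500/15,150 = 9.9%.
- Seeds also counted as receiving a kit: 1500/15,000 = 10.0%.
- 100 seeds (assumed upper value): 1400/15,000 = 9.3%.
- Calendar stop at N = 100 or N = 500 (illustrative): 85/1000 = 8.5%; 485/5000 = 9.7%.

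**Against the planned 70%.** 70% of 15,000 coupons is 10,500 kits. The cap is 1500 participants, and the estimated population is 6300 + 1400 = 7700.

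**What is cut off at the cap.** Waves start at 15, each is 10p times the one before, and the total is truncated at 1500. Lost redemptions are 15,000p − 1485.

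| True p | Reported | Last wave (no chance of redemption), % of coupons | Penultimate wave (partly truncated), % of coupons | Redemptions lost |
|---|---|---|---|---|
| 12% | 9.9% | 13% | 15% | 315 |
| 15% | 9.9% | 25% | 26% | 765 |
| 20% | 9.9% | 37% | 32% | 1515 |
| 30% | 9.9% | 60% | 27% | 3015 |

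At 30%, for example, the waves are 15, 45, 135, 405 and 900 (cut from 1215), and 900/1500 = 60%. At 70% the lost redemptions would be 10,500 − 1485 = 9015.

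**Simulation check.** Random redemption, 200 runs per rate and an assumed mean redemption delay of 14 days gave 9.9% in capped runs for every p from 12% to 90%.

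**Where the ratio does respond.**

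- *Chains die out (p below 10%).* The expected total is N = S/(1 − 10p), and putting this into the identity returns p. At p = 5%: N = 30 and 15/300 = 5%. Simulated means were 2.9%, 4.5% and 7.5% at p = 3%, 5% and 8%, with about 22 to 75 participants.
- *Repeat tests count.* With three repeat coupons for each of 1500 participants and a fraction r used, uptake = (1485 + 4500r)/19,500. This runs from 7.6% (r = 0) to 30.7% (r = 1).

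**The case against.** The strongest objection is about wording. The protocol often uses *distribute* for what participants do towards their peers. On that reading, coupons never passed on fall outside the denominator and the ratio is no longer tied to 9.9%. This stands as a limit: the result is conditional on counting issued coupons. However, the endpoint is not defined by hand-on to peers and no recording of hand-on is described. Coupons passed on but still open at the stop would remain a problem on either reading.

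Second, the stop applies to enrolment, and pharmacies must go on dispensing for 6-monthly tests. The protocol does not say whether those kits count. If they do, the ratio varies, but with repeat testing, and it reaches at most about 31%.

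Third, one might count the last two waves together as lost, which gives 87% of coupons at 30% redemption. The figures do not support that. The penultimate wave's 4050 coupons had already produced 900 of their 1215 expected redemptions (74%). Only the last wave, 60%, had no chance.

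Fourth, the identity fixes only the overall ratio. The planned paper and electronic strata can still differ from each other.

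Fifth, such detail might sit in an analysis plan, in operating procedures or in the recruitment figure, which is not shown. But coupon issue, the stop and the endpoint ratio are all set in this protocol, and an analysis-stage date filter is not enough if recruitment is fast. With an illustrative 56-day window and the assumed 14-day mean delay, it recovers 12.0% and 14.7% for true rates of 12% and 15%. At 30% or more the cap is reached in about 30 days or less and no coupon has matured.

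**Conclusion.** The point holds conditionally. If issued recruitment coupons form the denominator and repeat-test coupons and kits are left out, primary uptake stays below 10% at any stop (exactly 10.0% at the cap if seeds' own kits are counted). With 15 seeds it is about 9.9% at the cap, and 9.3% to 10.0% over an assumed 15 to 100 seeds, for any true redemption high enough to reach the cap. The planned 70% cannot appear, and the overall ratio cannot separate modest from high redemption.

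A reader might infer that the endpoint is uninformative under every reading and in every outcome. The documents do not support that. Below about 10% redemption the ratio tracks the true rate, although with few participants. The coupon-type strata can still be compared. Under the repeat-test reading the ratio can move between about 7.6% and 30.7%, which is still far below 70%. The ceiling is also not a product of the cap alone, since the same identity applies at a calendar stop. The wave shares assume deterministic growth.

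**What to change.** In sections 7 and 14, state that the primary ratio uses recruitment coupons only. Then:

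1. Give each recruitment coupon a fixed redemption window, printed on it.
2. Stop issuing recruitment coupons at a preset enrolment count or date. The trigger should not use expected redemptions, because that needs the rate being estimated.
3. Keep scanning coupons already issued for one full window, and record kits requested on them even if the cap has been reached.
4. Define the primary ratio as kits delivered or requested within the window, over coupons with a complete window.
5. Report the all-coupon ratio as a sensitivity result.

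The practical cost is coupon wording, a preset end to coupon issue, and issue and scan dates tied to the existing unique QR codes. Late enrolees would receive no recruitment coupons. The interval would be wider. If only earlier-wave coupons were kept at 30% redemption, 195 × 10 = 1950 of 15,000 coupons would remain, and √(15,000/1950) gives about 2.8 times the width on coupon count alone. Treating coupons as independent, the half-width would be 1.96 × √(0.30 × 0.70/1950) = 2.03 points, numerically similar to the precision the protocol already accepts.

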2 STUDY SYNOPSIS

[figure not shown]

Figure 1: study flow and recruitment process by respondent-driven sampling

3 SCIENTIFIC RATIONALE

The sharp rise in the number of new HIV infections among MSM in Asia has continued, and sexual activity between men remains stigmatized and often hidden. HIV prevalence among MSM was 5% or higher in 10 of the 24 countries that reported these data to UNAIDS in 2019 (1). About 30% of all new infections in Asia are in MSM. In the region, HIV incidence is high among young (15-24 years old) MSM; a recent publication reported an HIV incidence of 7.4 per 100 person-years in Bangkok in this population (2).

Similar to MSM's HIV infection, in Asia and the Pacific, it is widely reported that most new HIV infections will be among men who have sex with men and transgender people by the year 2020. Limited studies have been reported regarding HIV surveillance, HIV and STI prevalence, population size estimations, or behavior patterns for either transgender women or transgender men in the region. The most current data documenting HIV infection rates amongst transgender people only include transgender women in urban settings. Nevertheless, the data shows disturbing HIV infection rates throughout the region: Delhi 49%, Mumbai 42%, Phnom Penh 37%, Jakarta 34%, Surabaya 25%, Bandung 14%, Chaing Mai 18%, Phuket 12%, Bangkok 11%, Lahore 0.5% (3).

Version 1.1 du 18/04/2022

Late diagnosis is a serious barrier to tackling HIV. Around 69% of people living with HIV in the Asia and the Pacific region were aware of their status in 2018, up from 58% in 2015. However, this means around 1.9 million people did not know they were HIV positive.

Progress on testing varies greatly between countries. In Thailand, 94% of people living with HIV were aware of their status in 2018, as were 86% of people living with HIV in Malaysia and 82% in Cambodia. At the other end of the spectrum, only 37% of people living with HIV in Bangladesh and 14% of people in Pakistan were aware of their status.

Stigma, discrimination and punitive legal environments prevent many people from key populations from accessing testing services (4). Indeed in Malaysia and Sri Lanka, the HIV testing and awarness among MSM account for 43.3% and 40.3%, respectively while the HIV testing and awarness for TG people are 43% and 36.9%, respectively (5).

Despite Cambodia's admirable achievements the 90-90-90 targets by 2020, the HIV epidemic among key populations and, as yet, unidentified priority populations is an abiding concern. The latest available key-population data show HIV prevalence is 2.3% among men who have sex with men (MSM) and 5.9% among transgender women (TGW) (6,7). Despite this high prevalence rate, remain low the uptake of HIV testing among men who have sex with men (MSM<50%) and transgender women (TGW=39%) and consistent condom use (69% in MSM during anal sex and 38% for TGW with non-commercial sexual partners) (8). The IBBS 2019 report highlighted that about half of MSM and one third of TGW did not report any HIV testing or since more than 12 months. This suggests that undiagnosed HIV infection may persist in hard-to-reach MSM and TGW and new modality of HIV-testing approaches are hence needed to improve the uptake of HIV testing among these key populations. In addition, of those who reported HIV testing, the majority of MSM and TGW were tested at Community-based organizations (CBO) facilities (23.5% for MSM and 36.2% for TGW) and by CBO outreach workers (53.4% for MSM and 53.8% for TGW) while private facilities are poorly used for HIV (9).

From the perspectives of some users not only among general population but also "hidden" or "marginalized populations" such as MSM and TGW, results of HIV self-tests should be interpreted in private settings in order to guarantee complete anonymity. HIVST is a process in which an individual performs an HIV rapid diagnostic test (RDT) and interprets the result in private. Lav users can perform HIVST reliably and accurately and achieve performance comparable to that of trained health-care workers (10). HIV self-testing has the potential to increase the number of people living with HIV who have access to testing, know their status, are diagnosed and initiate treatment. HIV self-testing shares many characteristics with current HIV testing and counselling approaches, including products, accuracy issues, linkage to care, potential benefits and risks and regulatory policies and frameworks (11). Of some key populations, HIV self-testing increased testing frequency among high-risk MSM and could increase HIV diagnose in the trans community (12,13). In 2016, WHO recommended HIV self-testing (HIVST) as a safe, accurate and effective way to reach people who may not test otherwise, including people from key populations, men and young people (10). Representatives from 13 countries across Asia and the Pacific gathered to develop road maps to implement and expand pre-exposure prophylaxis (PrEP) and HIV selftesting in the region (14).

In 2017, Cambodia developed national consolidated guidelines on HIV testing services in which many approaches including HIV self-testing (HIVST) are recommended to increase the HIV test

Version 1.1 du 18/04/2022

uptake, especially among hard-to-reach and key populations (15). Recent evaluation of the B-IACM in Cambodia revealed that 66.5% who received assisted HIVST want to confirm their HIV status (16). Even though MSM and TGW had not heard about HIVST, all of them expressed willingness to try it (17).

While HIVST kits are distributed primarily from public health facilities, the HIVST is also available through private ways and channels. Some studies including the one conducted in Cambodia by Pal et al. (2016) suggested that men who have sex with men, transgender women wish or prefer HIVST to be available over-the-counter at pharmacies and other locations or through the Internet (17,18). HIVST is already formally and informally available, and it will likely become increasingly available. Indeed, HIVST kits are authorised to be dispensed from pharmacies in some countries such as USA and France (19,20). In addition, HIVST were reported informally on sale through the Internet and in pharmacies in many countries – with specific reports on this from Australia, China, Namibia, Peru, South Africa, Philippines and Malaysia (21).

Respondent driven sampling (RDS), a form of peer referral-based sampling, has become a popular strategy to recruit "hidden" or "marginalized populations" such as MSM and TGW. RDS implementation resembles snowball sampling with several critical caveats. Initial participants are purposefully recruited to be "seeds" as long as they fit the study's eligibility criteria. After completing the study procedures, seeds are offered a limited number of vouchers to recruit their peers to participate. When vouchers are redeemed, eligible participants also complete the same study procedures and are asked to recruit their peers, and this continues until recruitment goals are met. Using specially formulated statistical programs, sampling weights are developed and applied to estimate population parameters. For the purpose of RDS, effective seeds generate large recruitment chains and samples, which has been shown to be associated with motivation and a commitment to the research goals (22).

To mitigate some of the challenges of implementing the methodology, notably slow recruitment rates, innovation around conventional RDS can be helpful (23). Indeed, since there has been rise of using the Internet and online communities of gay and bisexual men in a few decades to facilitate new connections for the purpose of information seeking, socializing and seeking sex, several studies have reported innovative internet- and application-based RDS strategies in different aspects of AIDS/HIV research such as improving uptake of HIV self-testing among MSM, providing technical support, counselling and referrals for further HIV testing services, HIV prevention, care and treatment and other services (24–28).

Study main hypothesis

- The main hypothesis is that private pharmacies could be able to deliver HIV self-testing kits giving the advantage of confidentiality, anonymity and time-saving, which could be an effective intervention to improve HIV testing coverage for MSM/TGW.
- The second hypothesis is that a RDS method with a diversity of seeds recruited at hotspots and on social networks could help to identify a new network of hidden key population.

Version 1.1 du 18/04/2022

